8.1 Demographics, medical history and baseline characteristics

Demographics and medical history:

- Demographics: date of birth and/or age, sex, race and ethnicity (if allowed by local regulations).
- Relevant medical history (where possible diagnosis not symptoms must be recorded). Any new medical condition from informed consent signature must be reported as an AE.

Baseline characteristics:

- Underlying disease history including initial diagnosis and date of disease onset.
- Eastern Cooperative Oncology Group (ECOG) performance status for malignant diseases.
- Donor/graft characteristics: Donor type, HLA/gender match, source and number of stem cells, ABO compatibility, GvHD prophylaxis and type of graft manipulation.
- Infection positivity prior to HSCT.
- Type of conditioning (NMA, RIC, MAC).
- Vaccination history.

Reason for screening failure must be collected in the eCRF.

8.2 Prior and concomitant medications

Prior and concomitant medications (ongoing at screening) including previous medications/procedures used to treat the underlying disease and infection prophylaxis, type of conditions and vaccination history must be collected in the eCRF.

8.3 Clinical assessments

8.3.1 Vital signs

Vital signs will be measured at the visits as indicated in the assessments schedule (from Table 5a to Table 7b). Vital signs include body temperature, heart rate, systolic and diastolic blood pressure.

During the treatment period, heart rate and blood pressure must be measured pre-infusion (within 30 minutes from start of infusion) and at 1 and 2 hours post-infusion. Temperature can be measured pre-infusion only. More frequent measurements will be done in case this is medically indicated.

Any clinically relevant change in vital signs following signature of the informed consent form (ICF) should be collected as AE.

8.3.2 Height and weight

Height and body weight will be measured at the visits as indicated in the assessments schedule (from Table 5a to Table 7b).

Height will be measured at screening only. During treatment body weight must be measured within 24 hours prior to the planned infusion.

8.3.3 Physical examination

Physical examination will be performed as indicated in the assessments schedule (From Table 5a to Table 7b). A complete physical examination will be performed at screening, prior to HSCT, prior to treatment, at the last dosing day (dose 15) or EoT and at the follow-up visit 6 (week 24). During all other visits, the physical examination will be performed if medically indicated, based on medical history and symptoms or to follow up any abnormalities previously recorded as well as occurrence of new signs and symptoms. Physical examination must be documented in the relevant eCRF page.

Clinically relevant finding (other than the underlying disease) that are present prior to signing the informed consent must be recorded on the medical history page of the eCRF. Physical examination findings made after signing of informed consent, which meet the definition of an AE, must be recorded on the AE page of the eCRF.

8.3.4 Post-HSCT clinical assessments

Several clinical assessments are performed post-HSCT during monitoring, treatment and follow up. These assessments are reported in the assessment schedule under clinical assessments from Table 5a to Table 7b.

- Monitoring of occurrence of GvHD and/or engraftment syndrome, graft failure and graft rejection will be assessed during the monitoring, extended monitoring, treatment and follow-up period. Information on the severity and clinical characteristics of GvHD, engraftment syndrome, graft failure and graft rejection (in case of occurrence) will be collected in the eCRF.
- Re-occurrence or progression of the underlying malignant diseases will be monitored prior to treatment initiation, during treatment and follow-up period as indicated in the assessment schedule. Re-occurrence or progression of the disease will be assessed by measuring the minimal residual disease (MRD) in patients with malignant underlying disease.

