7.1 Efficacy

- Occurrence of primary GF from HSCT up to EoS visit.
- Occurrence of secondary GF from HSCT up to EoS visit.
- Occurrence of primary or secondary GFs from HSCT up to EoS visit.
- Occurrence of mixed donor chimerism <10% and <20% (based on unselected leukocytes or sorted T cells) from HSCT up to EoS visit.
- Occurrence of received transfusion of blood products due to poor graft function, hematopoietic growth factors, stem cell boost or DLI from HSCT up to 3 years follow up.
- Occurrence of receiving an additional allogeneic HSCT from HSCT up to 3 years follow up.
- Occurrence of poor graft function from HSCT up to EoS visit.
- Occurrence of event free engraftment from HSCT up to 3 years follow up.
- Occurrence of GvHD from HSCT up to 3 years follow up.
- Occurrence of engraftment syndrome from HSCT up to EoS visit.
- Occurrence of endothelial complications from HSCT up to EoS visit.
- Overall survival from HSCT up to 3 years follow up.

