7: The CXCL9 sample is analysed locally with a device provided by the Sponsor.

Table 6a: Schedule of assessments for Treatment period (Cohort 1, 2 and 3) – Patients weight \geq 30 kg

PERIOD (Duration)	TREATMENT ¹ (Up to 56 days)															EoT	
VISITS	Dose 1	Dose 2	Dose 3	Dose 4	Dose 5	Dose 6	Dose 7	Dose 8	Dose 9	Dose 10	Dose 11	Dose 12	Dose 13	Dose 14	Dose 15	Only for patients that discontinue treatment or engraft before dose 15	
Days \pm visit window	TD 0	TD 3	3 or 4 days from previous dose													3 days from engraftment (if before dose 15) or treatment discontinuation	
Study drug administration	X ²	X	X	X	X	X	X	X	X	X	X	X	X	X	X		
Anti-viral prophylaxis ³	X	X	X	X	X	X	X	X	X	X	X	X	X	X	X	X	
Clinical Assessments	Vital Signs ⁴	X	X	X	X	X	X	X	X	X	X	X	X	X	X	X	
	12-lead ECG	X														X	
	Chest X-Ray	Only in case of clinical suspicion of pulmonary infection														X	
	Physical Examination	X	As medically required														X
	Weight ⁵	X	X	X	X	X	X	X	X	X	X	X	X	X	X	X	X
Laboratory Procedures	Record GvHD, engraftment syndrome, GF, graft rejection	X	X	X	X	X	X	X	X	X	X	X	X	X	X	X	
	Biochemistry and hematology including differential hematology ⁶	X		X		X		X		X		X		X		X	
	ANC		X		X		X		X		X		X		X		
	Coagulation															X	
	MRD ⁷	X										X				X ⁸	
	Urine pregnancy test	X							X							X	
	Urinalysis	X	X	X	X	X	X	X	X	X	X	X	X	X	X	X	X
	Atypical Mycobacteria, Salmonella, Histoplasma, HZ	if an infection is suspected														X	
	HHV6, CMV, EBV, Adenovirus, Parvovirus	X	Repeat at dose 5 and dose 10 (only in patients positive to these infections prior to treatment) at all other visits only if an infection is suspected														X
	TB testing	X ⁹	if an infection is suspected														X
	Cells subsets	X		X ¹¹		X ¹¹		X ¹¹		X ¹¹		X ¹¹		X ¹¹		X ¹¹	X ¹¹
	Donor chimerism					X		X		X		X		X		X	X
	Inflammatory biomarkers ¹⁰	Pre/post	X	X	X	X	X	X	X	X	X	X	X	X	X	X	X
HLA antibodies against donor cells								X								X	
PK	Pre/	Pre/	Pre/	Pre/	Pre/		Pre/		Pre/		Pre/		Pre/		Pre/	X	

PERIOD (Duration)		TREATMENT ¹ (Up to 56 days)														EoT		
VISITS		Dose 1	Dose 2	Dose 3	Dose 4	Dose 5	Dose 6	Dose 7	Dose 8	Dose 9	Dose 10	Dose 11	Dose 12	Dose 13	Dose 14		Dose 15	
Days ± visit window		TD 0	TD 3	3 or 4 days from previous dose												3 days from engraftment (if before dose 15) or treatment discontinuation		
Antibodies against emapalumab		post X	post	post	post	post		post		post		post		post		post	X	X
AEs & Concomitant medications		X																

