10: Free IFN γ (pre-dose only before dose 1) and total IFN γ , CXCL9 and other inflammatory biomarkers in serum (e.g. IL-6, TNF α , Scd163 and Sil2R α).	

Table 7a: Schedule of assessments - Follow-up period, withdrawal visit, EoS and unscheduled visit (Cohort 1, 2 and 3) - Patients weight \geq 30 kg

PERIOD (Duration)	FOLLOW UP ¹ (3 years)											Unscheduled Visit ⁴
	FU 1 ¹	FU 2 ¹	FU 3 ¹	FU 4 ¹	FU 5 ¹	FU6 ¹ or EoS visit ^{1,2} or Withdrawal visit ³	Phone calls					
Days \pm window	Week 1 \pm 2 days	Week 2 \pm 2 days	Week 4 \pm 2 days	Week 8 \pm 1 week	Week 12 \pm 1 week	Week 24 \pm 2 Weeks	6 months \pm 2 weeks from HSCT ²	1 year \pm 4 week from HSCT ^{1,2}	2 year \pm 4 weeks from HSCT ^{1,2}	3 year \pm 4 Weeks from HSCT ^{1,2}		
Clinical Assessments	Vital Signs (BP, HR, body temperature)	X	X	X	X	X	X					X
	12-lead ECG											(X)
	Chest X-ray	Only in case of clinical suspicion of pulmonary infection					X					(X)
	Physical Examination	As medically required					X					X
	Weight	X	X	X	X	X	X					X
	Record engraftment syndrome			X	X	X	X					(X)
Laboratory Procedures	Record GvHD, GF, graft rejection	X	X	X	X	X	X					(X)
	Biochemistry and hematology including differential haematology ⁵	X		X	X	X	X					(X)
	Re-occurrence or progression of underlying malignant disease (MRD)			X	X	X	X					(X)
	Urine Pregnancy Test (if applicable)			X	X	X	X					(X)
	Urinalysis	X	X	X	X	X	X					(X)
	Search for infections ⁶	If an infection is suspected										(X)
	TB testing						X					(X)
	Cells subsets			X		X	X ⁸					(X)
	Donor chimerism			X	X	X	X					(X)
	Inflammatory biomarkers ⁷	X	X	X	X	X	X					(X)
	HLA antibodies against donor cells						X					(X)
	PK			X	X	X	X ⁸					(X)
	Antibodies against emapalumab			X		X	X ⁸					(X)
Survival check and GvHD occurrence recording											X	(X)
Relevant concomitant medications/procedures⁹	X										X	X
AEs	X										Only SAEs related to emapalumab	X

Table 7a Foot Notes
Abbreviations: FU: Follow Up; EoS: End of Study visit; BP: Blood Pressure; HR: Heart Rate; ECG: Electrocardiogram; MRD: Minimal Residual Disease; GF: Graft Failure; GvHD: Graft versus Host Disease; HLA: Human Leukocyte Antigen PK: pharmacokinetics; AEs: Adverse Events
1: This visit is foreseen for emapalumab treated patients. FU week 1 to be scheduled 1 week \pm 2 days from last study drug administration or 1 week after EoT (in case of treatment discontinuation or engraftment before the last dosing 15).

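### Tables 7a and 7b schedule no engraftment-syndrome record at FU1 and FU2, which leaves treated patients about three to four weeks without one after engraftment or the last dose

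*Combined protocol and SAP*

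**What the plan says.** Section 7.1 lists "Occurrence of engraftment syndrome from HSCT up to EoS visit" among the efficacy endpoints. Section 8.3.4 names engraftment syndrome with GvHD, graft failure and graft rejection and covers every period after transplant: "Monitoring of occurrence of GvHD and/or engraftment syndrome, graft failure and graft rejection will be assessed during the monitoring, extended monitoring, treatment". The same sentence goes on to include the follow-up period. The section adds that, when one of these events occurs, its severity and clinical features are entered in the eCRF. It refers to Tables 5a to 7b for the timing.

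The tables handle the event as follows:

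- **Tables 5a and 5b (monitoring and extended monitoring):** one row covers all four events. Extended-monitoring visits are every 7±1 days.
- **Tables 6a and 6b (treatment):** one row, "Record GvHD, engraftment syndrome, GF, graft rejection", is marked at every dose. The EoT cell cannot be read reliably in the extracted table.
- **Tables 7a and 7b (follow-up):** the row is split. "Record GvHD, GF, graft rejection" is marked at FU1 to FU6. "Record engraftment syndrome" is blank at FU1 and FU2, marked at FU3 to FU6, and optional at an unscheduled visit.

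Section 7.1 also lists "Occurrence of poor graft function from HSCT up to EoS visit" and "Occurrence of endothelial complications from HSCT up to EoS visit". No row of Tables 5a to 7b names either event, and 8.3.4 mentions neither.

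**The concern.** The two blanks apply to engraftment syndrome alone, and the protocol gives no reason for them. Under section 3.4.4 dosing stops once engraftment is confirmed, so FU1 and FU2 fall in the first weeks after engraftment for patients who respond. In those weeks a treated patient is not asked about the event, while an untreated patient in extended monitoring is asked weekly.

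Section 12.5 presents data by dose regimen, total emapalumab group and untreated group. A difference in engraftment-syndrome frequency between those columns could then partly reflect when the question was asked. Section 12.5.6 rules out imputation, so event details not collected at the time would not be made good in the analysis.

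**Working it through.** The plan states no figure on this point. The check compares the rows above and does date arithmetic on the visit windows.

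**Inputs**

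- Doses are 3 or 4 days apart (section 5.4), so the last dose L falls 0 to 4 days before confirmed engraftment E.
- EoT is 3 days after engraftment if that comes before dose 15 (Tables 6a and 6b), so EoT = E+3. Patients who complete dose 15 have no EoT visit (section 3.4.4).
- FU1, FU2 and FU3 are 1, 2 and 4 weeks after the last dose, each ±2 days (section 3.4.5). FU1 may instead be 1 week after EoT.
- Extended-monitoring visits are every 7±1 days (Tables 5a and 5b).

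**Gap for a patient who stops at engraftment, EoT counted as a record**

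- Earliest FU3: E − 4 + 28 − 2 = E+22. Latest FU3: E + 0 + 28 + 2 = E+30.
- Gap from EoT: 22 − 3 = 19 days to 30 − 3 = 27 days.

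**Gap if EoT does not record the event, or there is no EoT visit after dose 15**

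- From the last dose to FU3: 28 − 2 = 26 days to 28 + 2 = 30 days.

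**Same span in an untreated patient in extended monitoring**

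- One record every 6 to 8 days. Over 19 to 27 days at a 7-day interval: 19/7 ≈ 2.7 to 27/7 ≈ 3.9, so about three or four records against none.

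**With FU1 and FU2 marked**

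- FU1 falls at E − 4 + 5 = E+1 to E+9, or E+10 if set from EoT. FU2 falls at E − 4 + 12 = E+8 to E+16.
- FU2 to FU3 is at most (28 + 2) − (14 − 2) = 18 days, the longest interval left in this stretch.
- Scheduled follow-up records rise from 4 of 6 to 6 of 6, matching GvHD, graft failure and rejection.

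**The other two endpoints:** named rows in Tables 5a to 7b number 0, for treated and untreated patients alike.

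**The case against.** The strongest reply is that nothing is shown to be lost. Adverse events are collected to EoS in both groups (section 9.1.4), and any new medical condition after consent is an adverse event (section 8.1). FU3 can pick up events from the preceding weeks, and an unscheduled visit may record the syndrome. Section 8.3.4 calls for severity and characteristics whenever an event occurs, not only at ticked visits. Confirmed engraftment also needs three consecutive ANC values (section 3.4.4), so recovery starts while the event is still being recorded at each dose. All of this stands. It reduces the concern to a risk, but it does not explain why one of four grouped events is left out at two visits.

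A reader might infer more than the documents support:

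- **That FU1 and FU2 are the first two visits after treatment stops at engraftment.** Patients who stop before dose 15 attend EoT first. Only those who complete dose 15 go straight to FU1.
- **That 8.3.4 contradicts Tables 7a and 7b.** It says the event is assessed in follow-up and leaves timing to the schedule, which marks FU3 to FU6.
- **That all three endpoints are under-ascertained, unevenly by group.** Under-ascertainment is not demonstrated for any of them. The missing rows for poor graft function and endothelial complications affect both groups alike.
- **That poor graft function cannot be derived from laboratory data.** At 30 kg and above, Table 5a schedules ANC throughout, hematology in extended monitoring, and chimerism at seven monitoring visits and in extended monitoring. Concomitant medications are recorded in both groups, and transfusion, boost, DLI and hematopoietic agents at follow-up. Below 30 kg the basis is thinner: Table 5b keeps ANC, but has hematology only at screening and chimerism as clinically indicated.
- **That the two endpoints should be dropped.** The protocol defers detail to a SAP. Neither a separate SAP nor the eCRF is in the text examined, and either may define the terms and their source. Dropping exploratory secondary endpoints for this would be disproportionate.

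Two further points limit the consequence. Section 12.4 assigns efficacy endpoints to the all treated population, so the untreated column for this endpoint rests on the general statement in section 12.5. The EoS windows also differ more than the visit marks do. Untreated patients finish by about day 98 + 3 + 7 = 108. A patient treated for primary GF from day 43 can run to about day 43 + 55 + 168 + 14 = 280, and marking FU1 and FU2 does not change that.

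**Conclusion.** The point holds as a small schedule gap. Treated patients have no scheduled engraftment-syndrome record for about 19 to 27 days between EoT and FU3, or 26 to 30 days from the last dose where EoT does not record the event or does not take place. Untreated patients in extended monitoring are asked every 6 to 8 days. The result is a risk of uneven ascertainment in a secondary, descriptive endpoint. The main efficacy endpoint, primary GF from start to end of treatment, is not touched.

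The size rests on three assumptions: FU3 is counted from the last dose, as section 3.4.5 states; the single mark in Tables 5a and 5b covers both monitoring periods, consistent with 8.3.4; and the EoT cell, which is unclear in the extracted table, is bracketed by the two ranges. How much the gap matters also depends on engraftment syndrome clustering around neutrophil recovery, which the documents do not state.

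For poor graft function and endothelial complications, what is missing is a named place or source of recording, in both groups. That is mainly missing detail.

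**What to change.** Mark engraftment syndrome at FU1 and FU2 in both Table 7a and Table 7b, most simply by merging its row with the GvHD, graft failure and rejection row, or state why those visits are left out. Both visits already take place and already record the other three events, so the cost is schedule and eCRF wording, with no new visit or sample.

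As a minor addition, name the data source for poor graft function and endothelial complications in the protocol or SAP, with a definition of each if none exists there. Alternatively, add both to 8.3.4 and the existing event-recording rows of Tables 5a to 7b. Either way, do the same for treated and untreated patients. The cost is again wording only.

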8.3.5 Chest X-ray

A chest X-ray will be performed as a measure for detection of pulmonary infections and will be performed at screening, EoT and follow-up visit 6 (week 24). A chest X-ray should be done any time there is a clinical suspicion of pulmonary infection based on medical judgment.

Refer to Section 3.4.1 Screening period for acceptance criteria of previously performed chest X-rays for screening or re-screening.

8.3.6 ECG

A 12-lead electrocardiogram (ECG) will be performed at screening, prior to treatment and EoT. The ECG will be interpreted locally by the investigator or delegate.

Clinically relevant ECG findings that are present prior to informed consent signature must be recorded in the medical history section of the eCRF. Clinically relevant findings found after informed consent signature must be reported as an AE.

8.4 Laboratory assessments

In accordance with current regulations (ICH E11, 20 July 2000), blood sampling in infants and children must be done by using micro-sampling techniques in order to minimize as much as possible the blood drawn and/or the number of venipunctures.

The amount of blood foreseen to be drawn during the study remains below the limits recommended by existing guidelines for blood sample volume limits (WHO | Blood Sample Volumes in Child Health Research: Review of Safe Limits). The amount of blood has been estimated by assuming the scenario of a patient remaining in each study period for the maximum duration of each period i.e. up to 42 days in monitoring period, up to 98 days extended monitoring and dosed every 3 or 4 days for up to 15 infusions and completing the follow-up period of 24 weeks. It is expected that patients will remain in each period less than the maximum duration.

Laboratory assessments have been minimized in infants and children according to body weight. Laboratory parameters will be assessed during the study at the time points detailed in Table 5a, 6a, 7a for patient of weight ≥ 30 kg and in Table 5b, 6b, 7b for patients of weight < 30 kg. Some assessments are not performed in patients of weight < 15 kg and these are indicated with an (*) in the assessment schedule.

The laboratory parameters to be assessed during the study are listed below. Details on which parameters will be performed locally will be provided in a laboratory manual.

- Hematology: hematocrit, hemoglobin, platelets, red blood cells (RBC), white blood cells (WBC).
- Hematology differential: lymphocytes, monocytes, neutrophils.
- Biochemistry: ferritin, glucose, C-reactive protein (CRP), sodium, potassium, chloride, calcium, magnesium and phosphate, aspartate aminotransferase (AST), alanine aminotransferase (ALT), gamma-glutamyl transpeptidase (γ GT), alkaline phosphatase (ALP), lactate dehydrogenase (LDH),

bilirubin (total, direct and indirect), triglycerides, cholesterol (total and high-density lipoprotein [HDL]), albumin, creatinine, urea (fasting conditions whenever possible).

- Coagulation tests: activated partial thromboplastin (aPTT), prothrombin time (PT).
- Urinalysis: glucose, blood, protein, leucocytes, ketones, pH and specific gravity.
- Serum pregnancy test (if applicable).
- Urine pregnancy test (if applicable).
- Donor chimerism.
- HLA antibodies against donor cells.
- MRD (in malignant patients only).

Any clinically relevant change in laboratory assessment following signature of the ICF should be collected as an AE. Details on sample preparation and handling will be described in a laboratory manual.

8.4.1 Search for infections

Infection search will be performed during the study at the time points as detailed in the assessments schedule (Table 5a, Table 6a and Table 7a for patient of weight ≥ 30 kg and in Table 5b, Table 6b and Table 7b for patients of weight < 30 kg). Some assessments are not performed in patients of weight < 15 kg and these are indicated with an (*) in the assessment schedule.

Search for infections include the following pathogens:

- **Atypical mycobacteria, Salmonella, Histoplasma capsulatum, Herpes zoster**

Patients with clinical manifestations of any of these infections prior to HSCT are not eligible.

Patients presenting with clinical manifestations of these infections prior to treatment (TD0) **must not be treated**.

- **Mycobacterium tuberculosis**

- **At screening**

TB testing at screening will be performed via IFN γ -release assay or PPD test. In the case of a patient having received BCG vaccination, a PPD test must be performed and combined with IFN γ -release assay if the PPD result ≥ 5 mm.

Results of the TB testing performed at screening must be available prior to HSCT for eligibility assessment. Patients presenting active or clinical suspicion of latent TB are not eligible to enter the study.

In addition, a baseline sample via polymerase chain reaction [PCR] in any relevant specimen (e.g., urine or blood, if sputum is not easily obtained) has to be obtained, as this test will be used starting from emapalumab treatment initiation to perform regular TB monitoring.

- **Prior to treatment**

TB testing is repeated prior to treatment only in the case the test at screening is older than 30 days or if there is clinical suspicion on TB.

The TB test prior to treatment should be performed with PCR only.

Availability of the results of the TB test (if repeated prior to emapalumab administration) is not required provided that (i) results from the test performed at screening are available (ii) the microbiological analysis of the sample collected prior to treatment is ongoing and (iii) the patient clinical condition is not indicative of the presence of an active infection.

Patients with clinical manifestations of TB prior to treatment **must not be treated**.

- **At all the other visits**

At all other visits TB testing is performed with PCR only.

- **Human Herpes virus 6 (HHV6), cytomegalovirus (CMV), Epstein-Barr virus (EBV), adenovirus and parvovirus**

These infections will be monitored during the study in order to collect information to interpret potential influence on the HSCT outcome and to monitor any infection re-activation due to the interferon gamma inhibition.

Details on sample preparation and handling for search for infections will be described in a laboratory manual.

